11.0 Study Timelines

11.1 Describe the anticipated duration needed to enroll all study subjects.

Response:

We anticipate it will take about 5 years to enroll all study subjects, with enrollment of each cohort taking about 3-4 months.

11.2 Describe the duration of an individual subject's participation in the study. Include length of study visits, and overall study follow-up time.

Response:

Pilot Phase: Children will participate individually in one in-restaurant taste test session for up to 30 minutes.

Experimental Phase: Families will be recruited and enrolled during the recruitment & initial assessment period which will occur across a span of about 3-4 months per cohort. In the subsequent exposure period (a predetermined period of about 2 months to follow recruitment), families will return 6 times to the restaurant they were recruited in for a meal and will complete a brief online survey (<20 min). After this, families will return once during a predetermined period of up to 3 months for a final meal and assessment. Families will also be prompted to complete an online survey about their child's dietary intake the day after the last session. Across study periods, each family will participate for about 6 months total. The total duration of participation is the same for families recruited remotely, with minor differences in specific procedures as described herein.

11.3 Describe the estimated duration for the investigators to complete this study (i.e. all data is collected and all analyses have been completed).

Response:

We estimate it will take about 6 years to complete this study.

12.0 Setting

12.1 Describe all facilities/sites where you will be conducting research procedures. Include a description of the security and privacy of the facilities (e.g. locked facility, limited access, privacy barriers). Facility, department, and type of room are relevant. Do not abbreviate facility names.

NOTE: Examples of acceptable response may be: "A classroom setting in the Department of Psychology equipped with a computer with relevant survey administration software," "The angiogram suite at Buffalo General Medical Center, a fully accredited tertiary care institution within New York State with badge access," or, "Community Center meeting hall."

Response:

Pilot Phase: Research will be conducted at 1-3 Anderson's restaurant locations in the Western New York area. Anderson's is a quick-service restaurant open to the public.

Experimental Phase: Research will be conducted at all of Anderson’s restaurant locations in the Western New York area. At the time of this writing, there are 6 locations.

12.2 *For research conducted outside of UB and its affiliates, describe:*

- *Site-specific regulations or customs affecting the research*
- *Local scientific and ethical review structure*

NOTE: This question is referring to UB affiliated research taking place outside UB, i.e. research conducted in the community, school-based research, international research, etc. It is not referring to multi-site research. UB affiliated institutions include Kaleida Health, ECMC, and Roswell Park Cancer Institute.

Response:

The sites for both research phases are local restaurants in the Western New York area. All restaurant sites adhere to health standards and codes. The study will be conducted with approval of the restaurant owner and specific location managers. The restaurant does not require its own ethical review process, so the sole review process will be that of the UB IRB.

☐ N/A: This study is not conducted outside of UB or its affiliates.

13.0 Community-Based Participatory Research

13.1 *Describe involvement of the community in the design and conduct of the research.*

NOTE: Community-Based Participatory Research (CBPR) is a collaborative approach to research that equitably involves all partners in the research process and recognizes the unique strengths that each brings. CBPR begins with a research topic of importance to the community, has the aim of combining knowledge with action and achieving social change to improve health outcomes and eliminate health disparities.

Response:

☒ N/A: This study does not utilize CBPR.

13.2 *Describe the composition and involvement of a community advisory board.*

Response:

☒ N/A: This study does not have a community advisory board.

14.0 Resources and Qualifications

14.1 *Describe the qualifications (e.g., education, training, experience, expertise, or certifications) of the Principal Investigator **and** staff to perform the*

research. When applicable describe their knowledge of the local study sites, culture, and society. Provide enough information to convince the IRB that you have qualified staff for the proposed research.

NOTE: If you specify a person by name, a change to that person will require prior approval by the IRB. If you specify a person by role (e.g., coordinator, research assistant, co-investigator, or pharmacist), a change to that person will not usually require prior approval by the IRB, provided that the person meets the qualifications described to fulfill their roles.

Response:

All faculty, staff, and students on this protocol have completed CITI training, and all personnel interacting with children will also undergo a Background Check prior to their first data collection session, which is standard procedure for our team. At least one team member with CPR/first aid training will be at every data collection session, and multiple team members will be present at every in-person data collection session.

For remote data collection, teams will be assigned so that ~2 study staff are assigned to be “on call” during times that the participants may be in the restaurant completing study procedures, to assist as appropriate. We have set up our screening procedures so that only potential participants contacting the study team during times we plan to be available to provide support (approximately 4:30-8:30pm) will receive a link to the screening questionnaire, to ensure that we are available to support those who move forward to consent and baseline procedures. Postdoctoral associate, [name], has experience providing support electronically during similar remote data collection and will serve as a project manager, training others on protocols and providing oversight (along with the PI).

[name] (PI) has extensive experience working with parents and children and has experience in behavioral research using similar methodology to that included in this study, including collecting data from families in Anderson’s and other restaurants. [name] has extensive experience with child eating behavior research, and [name] has experience with community research related to healthy eating.

Describe other resources available to conduct the research.

14.2 Describe the time and effort that the Principal Investigator and research staff will devote to conducting and completing the research.

NOTE: Examples include the percentage of Full Time Equivalents (FTE), hours per week. The question will elicit whether there are appropriate resources to conduct the research.

Response:

It is planned for the PI to devote about 40% effort to this study while it is taking place, leading and managing the project.

Co-investigators [name] and [name] will devote about 10% and 20% effort respectively as co-investigators. Their primary roles are in the areas of study design and data interpretation. [name] will devote 10% time as data manager.

Other research staff/students will devote between 5-40 hours a week to this project, depending on their specific role. Their primary roles will be recruitment, data collection, and data entry.

14.3 Describe the availability of medical or psychological resources that subjects might need as a result of anticipated consequences of the human research, if applicable.

NOTE: One example includes: on-call availability of a counselor or psychologist for a study that screens subjects for depression.

Response:

We do not anticipate that subjects will need medical or psychological resources as a result of the study. Personnel certified in cardiopulmonary resuscitation (CPR) and first aid will be present during in-person assessments, and these individuals are trained to contact appropriate emergency medical personnel in the case of a serious event.

14.4 Describe your process to ensure that all persons assisting with the research are adequately informed about the protocol, the research procedures, and their duties and functions.

Response:

All personnel working on the project are required to complete the CITI training as required by IRB. Additionally, there are procedure manuals that are read and followed by all personnel. The PI and Project Coordinators are responsible for training all staff on data collection and recording procedures.

15.0 Other Approvals

15.1 Describe any approvals that will be obtained prior to commencing the research (e.g., school, external site, funding agency, laboratory, radiation safety, or biosafety).

Response:

The owner of Anderson's restaurant has indicated her approval in partnering with us on this study. She submitted a letter of support to us at the time of our NIH grant submission and has confirmed her continued interest and support prior to each study phase to date, with our most recent communication indicating her continued support in April 2022.

☐ N/A: This study does not require any other approvals.

16.0 Provisions to Protect the Privacy Interests of Subjects

16.1 *Describe how you will protect subjects' privacy interests during the course of this research.*

NOTE: Privacy refers to an individual's right to control access to him or herself. Privacy applies to the person. Confidentiality refers to how data collected about individuals for the research will be protected by the researcher from release. Confidentiality applies to the data.

Examples of appropriate responses include: "participant only meets with a study coordinator in a classroom setting where no one can overhear", or "the participant is reminded that they are free to refuse to answer any questions that they do not feel comfortable answering."

Response:

In both study phases all recruitment details will be kept confidential and private. Participants may complete the screening of their own free will, and thus are controlling access to their privacy. Participants will be reminded they have the right to refuse to answer any question that makes them uncomfortable, and prefer not to answer is an option on all sensitive survey questions. None of the questions that we plan to administer verbally in the public restaurant space are considered sensitive (nonetheless, participants have the option to opt out of these and any other questions/procedures involved in the study if they chose to do so). Study staff will be trained to discreetly collect the foods needed for the plate waste measurements with the goal to ensure the comfort and privacy of the participants.

16.2 *Indicate how the research team is permitted to access any sources of information about the subjects.*

*NOTE: Examples of appropriate responses include: school permission for review of records, consent of the subject, HIPAA waiver. This question **does apply** to records reviews.*

Response:

N/A, we will not be accessing any sources of information about the subjects.

17.0 Data Management and Analysis

17.1 *Describe the data analysis plan, including any statistical procedures. This section applies to both quantitative and qualitative analysis.*

Response:

Pilot Phase: Child feedback will be used to determine which food components will be used in the experimental phase.

Experimental Phase: Descriptive statistics, normality plots, and study group differences will be examined for all variables, with results informing analyses (e.g., using non-parametric statistics if appropriate). Planned analyses corresponding to each aim are described below. Analyses incorporate random effects for restaurant location as required in cluster-randomized trials.

Aim 1. A mixed model with a binomial distribution will test whether intervention children are more likely to order a healthier promoted meal compared to controls,

with study group, time point (initial, mid1-mid6, and post), and the group-by-time interaction as fixed effects, a random effect for restaurant location, and a contrast focused on study group differences at post. Mixed models with linear distributions will compare the groups on calories, saturated fat, sodium, and sugar ordered, with the same factors. We will use sales data and chi-square analyses to compare the percentage of kids' meals ordered that were healthier featured meals in intervention versus control restaurants across the study period and separately by recruitment, exposure, and redemption periods. We will also summarize child and parent orders at each time point and the frequency of behaviors of interest (e.g., who ordered for the child) during parent-child interactions in intervention and control groups and will compare the number of kids' meals ordered in each group of restaurants against initial sales data from parallel time periods one year prior, overall, by cohort, and by recruitment, exposure, and redemption periods.

Aim 2. We will use mixed models with linear distributions to compare study groups on calories, saturated fat, sodium, and sugar consumed in the restaurant, with study group, time point (initial, post), and the group-by-time interaction as fixed effects and a random effect for restaurant location. We will repeat these analyses using data from repeat 24-hour dietary recalls to examine intervention effects on daily energy, saturated fat, sodium, and sugar intake among participating children (post-test only). We will also explore associations between ordering of the promoted meals and children's dietary intake within the meal and total day and will repeat aforementioned models testing intervention effects on orders and intake, incorporating child sex, age, and weight status (overweight/obese vs. normal weight) as potential covariates and effect moderators. We will also plan ancillary analyses that explore dining at Anderson's locations besides the assigned location and number of exposures as additional factors in the mixed models described above; if there are substantial missing data on number of exposures, we can treat this variable as categorical with "missing" retained as a category, to retain our sample size. Finally, if substantial demographic differences between groups are revealed, we will incorporate propensity scores into our analyses to account for this potential source of bias. Analyses will incorporate multiple imputation methods as appropriate, depending on the extent of missing data.

17.2 If applicable, provide a power analysis.

NOTE: This may not apply to certain types of studies, including chart/records reviews, survey studies, or observational studies. This question is asked to elicit whether the investigator has an adequate sample size to achieve the study objectives and justify a conclusion.

Response:

Pilot Phase: No power analysis is required for this qualitative exploratory phase.

Experimental Phase: To determine the sample size needed to test effects on orders of healthier meals, we used findings from our preliminary research, showing that 27.8% of participants exposed to study placemats and 6.7% of the control group ordered the featured healthier entrees (1). Using these values, an alpha of .05,

power of 80%, 6 cluster, and an intraclass correlation of .01 based on prior restaurant research (2), it is estimated that 124 participants will be needed to test intervention effects on meal selection.

Repeating this calculation for calories consumed in the restaurant (Aim 2), we used calories consumed among children ordering a healthier entrée (473.3 ± 197.4) or less healthy entrée (556.6 ± 199.4) in our preliminary research and the same alpha, power, intraclass correlation, and cluster values used above for an estimate of 684 participants ($d=.42$). To retain adequate power in the event that some recruited participants do not return at post-test, we increased this estimate by ~35%, a figure informed by show rates from prior restaurant research (3), for a final target sample of 930 families (465 per study group).

References:

17.3 Describe any procedures that will be used for quality control of collected data.

Response:

All data will be entered and quality controlled by trained staff. Data that are entered manually, which in this study includes entering data from study forms (experimental phase; e.g. plate waste measurements) will be double entered by study staff, with double entry compared and cleaned as needed.

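### Six restaurants leave 4 degrees of freedom for the arm contrast; section 17.1 names none, and the 124 and 684 in section 17.2 rest on different ones

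*Combined protocol and SAP*

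**What the plan says.** Section 4.1 pairs six restaurants by area income and randomises one of each pair to each arm.

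Section 17.1 deals with clustering in one sentence: "Analyses incorporate random effects for restaurant location as required in cluster-randomized trials". The Aim 1 models have group, time (eight points), group-by-time and a random effect for restaurant, with a contrast at post. The Aim 2 models have the same structure with two time points. No test statistic, estimation method (ML or REML), denominator degrees of freedom or small-sample correction is named. There is no restaurant-by-time, child or pair term.

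Section 17.2 sizes meal selection from the finding that "27.8% of participants exposed to study placemats and 6.7% of the control group ordered the featured healthier entrees", with an alpha of .05, "power of 80%, 6 cluster, and an intraclass correlation of .01 based on prior restaurant research", and concludes that "it is estimated that 124 participants will be needed to test intervention effects on meal selection". It then sizes calories consumed from 473.3 ± 197.4 against 556.6 ± 199.4, with "the same alpha, power, intraclass correlation, and cluster values used above for an estimate of 684 participants". The 930 target is the 684 raised by about 35% for non-return.

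**The concern.** A random intercept lets the model estimate how much restaurants differ. It does not allow for that variance being estimated from six units. The allowance comes from the reference distribution, and the plan leaves that open. The same data and the same written model can be judged against 1.96 or against 2.78 (t on 4 df), and a result between the two would be significant or not according to a software option.

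This touches the primary outcomes: H1a in the binomial model, and calories, saturated fat, sodium and sugar ordered in the linear models. It also bears on whether section 17.2 describes the test that will be run. The larger of its two figures already assumes 4 df, and the smaller does not.

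**Working it through.** **Inputs (section 17.2).** Alpha .05 (two-sided assumed; it reproduces both figures), power 80%, 6 restaurants, ICC .01. Rates .278 and .067. Calories 473.3 (SD 197.4) and 556.6 (SD 199.4).

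**Formulas.** For N children in total, m = N/6 and DE = 1 + (m − 1)(.01). SE = √(4·V·DE/N), λ = difference/SE. Power is that of a two-sided noncentral t with ν degrees of freedom.

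**Reproducing 684.** V = (197.4² + 199.4²)/2, so SD = 198.4. The difference is 83.3 (d = .42).
- N = 684: m = 114, DE = 2.13, SE = 22.14, λ = 3.762. With ν = 6 − 2 = 4 (critical value 2.776), power is 80.02%.
- N = 678 gives 79.9%. So 684 is the smallest multiple of six that reaches 80% on 4 df.
- On individual-level df (ν = N − 2), about 254 children would have been enough.

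**Reproducing 124.** Mean rate .1725; pooled V = .1725 × .8275 = .1427; difference .211.
- N = 124: m = 20.67, DE = 1.197, SE = .0742, λ = 2.843. With ν = 122, power is 80.5%; N = 122 falls just short.
- Another route also gives 124: a continuity-corrected 59 per arm times 1.05, which reads 6 as the cluster size. It uses no restaurant-level df either.

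**124 on the basis of 684 (ν = 4).**

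| N | Variance | λ | Power on 4 df |
|---|---|---|---|
| 124 | pooled | 2.84 | 58% |
| 124 | unpooled (.1316) | 2.96 | 61% |
| 230 | unpooled | 3.76 | 80% |
| 258 | pooled | 3.76 | 80% |
| 684 | pooled | 5.00 | 95.5% |
| 684 | unpooled | 5.21 | 96.7% |

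Rounding 230 up to equal restaurants gives 234.

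**Null rejection rate if the contrast is referred to z.** These are simulations with 3 restaurants per arm, 114 children per restaurant, ICC .01 and nominal 5%.

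| Model | REML | ML |
|---|---|---|
| Linear, 8 time points | 7.2% | 9.6% |
| Linear, 2 time points | 8.0% | 11.0% |
| Linear, 8 points, restaurant-by-time variance .01 added | 11.4% | 15.0% |
| Linear, 2 points, restaurant-by-time variance .01 added | 10.9% | 15.1% |

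The rows with added variance also assume a child-level correlation of .3. Without the added variance, that correlation lowers the 8-point REML figure to 5.9%.

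For the binomial model with 8 time points, runs at ICC .01 ranged from about 8% to 14%. Part of the spread is whether .01 is read on the proportion or the logit scale. Part is numerical: 21 fixed quadrature nodes are too coarse with 114 × 8 = 912 observations per restaurant, and they gave 12% to 13%. Adaptive quadrature (8,000 runs per setting) gave 9.0% on the proportion scale, at null rates of both 6.7% and 17%, and 7.3% on the logit scale. With an assumed restaurant-by-time variance of .01, the rate was 13% to 16%.

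As a ceiling for an intercept-only linear model, a large ICC gives P(|t₄| > 1.96) = 12% under REML. Under ML the variance shrinks by 4/6, so P(|t₄| > 1.96·√(4/6) = 1.60) = 18%.

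**Is t on 4 df the remedy inside the stated model?** Not by itself. In the intercept-only model it rejected in about 1% to 4%. The variance of the post contrast is partly within-restaurant and well estimated. For 8 time points, the between part is .01 + .99/912 = .0111 of a total .01 + .99/114 = .0187. A Satterthwaite calculation then gives 4 × (.0187/.0111)² ≈ 11 df; for 2 time points it gives about 7. Kenward-Roger in that model would therefore not return 4 df. A restaurant-level t-test on 4 df rejected in 4.8% to 5.2% of null data sets in every linear scenario simulated.

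**The case against.** The plan never says that a Wald z test will be used. A reader might infer that H1a will run at two to four times its nominal level. The documents do not support that: they are silent, and every rate above is conditional on a choice not yet made. A rate of 20% also needs something the plan does not give, such as restaurant-by-time variance of about .02 with ML. At the stated ICC the inflation is modest, and under REML in the 8-point linear model it is small.

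A reader might also infer from the 124 that the trial is too small. It is not, on the plan's own assumptions. The 930 is built on 684, which already uses 4 df, and meal selection has about 96% power there. Nor does the plan state a method that 124 violates; the 4 df is inferred from reproducing 684.

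All of this stands. What remains is the silence on degrees of freedom with six clusters, and two figures presented as one calculation that do not share a basis.

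**Conclusion.** The point holds in conditional form and is a should-fix. Section 17.1 does not fix the reference distribution for its arm contrasts. A large-sample Wald test at ICC .01 would reject a true null in about 7% to 11% of trials in the linear models. For the binomial model the runs spanned 8% to 14%, and I put most weight on about 9%. Variation between restaurants over time, which the stated models omit, raises these rates. In section 17.2, 124 does not deliver 80% power on the degrees of freedom behind 684; it delivers 58% to 61%.

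Assumptions: two-sided testing, equal restaurants, ICC .01, and the simulated null rates. The restaurant-by-time variances are illustrative, since the documents give none.

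**What to change.** 1. In 17.1, state that the post-test arm contrast is tested on between-restaurant degrees of freedom, with a restaurant-level t-test on 4 df (2 if pair is fitted) as the reference or confirmatory test. Add a restaurant-by-time term to the mixed models. Use REML with Kenward-Roger for the linear models, and a between-restaurant t reference rather than z for the binomial model. Name the estimation method.
2. State in advance whether pair is fitted. The 684 presupposes 4 df. On 2 df (critical value 4.30), the same λ values give about 52% power for calories and 72% to 75% for meal selection at 684, unless pairing removes between-restaurant variance.
3. In 17.2, replace 124 by about 230 (unpooled variance) to 258 (pooled), on the same 4-df basis as 684.

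The cost is wording, best settled before outcome data are seen. The 930 target does not change. Confidence intervals widen (2.78 in place of 1.96), and the t reference is somewhat conservative in the mixed models when the ICC is small.

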1.0 Objectives

1.1 Describe the purpose, specific aims, or objectives of this research.

Response:

Pilot Phase: The purpose of this phase is to conduct taste tests to determine children's reactions to foods that are being considered for the subsequent experimental phase.

Experimental Phase: The objective of this research is to make healthier kids' meal options more appealing and easier to choose via an in-restaurant intervention that combines repeated exposure and choice architecture strategies. This phase has 2 main aims:

Aim 1: To test effects of a healthier kids' meal intervention on children's meal orders.

Aim 2: To test effects of a healthier kids' meal intervention on children's dietary intake.

1.2 State the hypotheses to be tested, if applicable.

NOTE: A hypothesis is a specific, testable prediction about what you expect to happen in your study that corresponds with your above listed objectives.

Response:

Pilot Phase: There is no explicit hypothesis during this exploratory pilot phase.

Experimental Phase:

Hypothesis 1a: 4-to-8-year-old study participants in intervention restaurants will be more likely than controls to select one of the promoted healthier kids' meals at post-test.

Hypothesis 1b: 4-to-8-year-olds in the intervention group will order fewer calories and desserts and less saturated fat, sodium and sugar at post-test versus controls.

Hypothesis 1c: The promoted healthier meals will make up a greater percentage of kids' meals ordered in intervention restaurants versus controls, based on sales data across the study period.

Hypothesis 2: Compared to controls, 4-to-8-year-old study participants in the intervention group will consume fewer calories and less saturated fat, sodium, and sugar in the restaurant at post-test.

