4.0 Study Design

4.1 Describe and explain the study design (e.g. case-control, cross-sectional, ethnographic, experimental, interventional, longitudinal, observational).

Response:

Pilot Phase: A cross-sectional study design will be used. About 25 children from 1-3 restaurant locations will participate in taste tests to inform food selections for the subsequent experimental phase. Families will be asked if they want to

participate in taste tests during a regular visit to a location of the study restaurant (Anderson's Frozen Custard). Participating children will taste up to 5 side dishes (e.g. applesauce, carrot sticks, mandarin oranges) and up to 5 main dishes (e.g. turkey sandwich, peanut butter and banana sandwich). They will then use a visual face scale to rate their liking and rank ordered preferences for presented options and be asked for their opinions on the foods (e.g., why they liked/disliked the food items). Parents will be asked to complete a brief demographic survey on an electronic tablet or with pen and paper.

Experimental Phase: A cluster-randomized design will be used. 6 locations of Anderson's, a regional quick-service restaurant in the Buffalo, New York, area will be paired based on income levels in the surrounding census tracts. A location from each pair will be randomized to each study group (intervention, control). Recruitment and data collection will be conducted across about 3 to 5 cohorts, with recruitment conducted either in person or remotely during a family's regular visit to Anderson's.

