Observations of Family Interactions. Parent-child interactions will be unobtrusively observed in a random subsample during the exposure period. Two study staff members will be at a table in the restaurant to unobtrusively observe parent-child interactions, for a total of about 10 minutes (about 5 minutes before the meal and about 5 minutes during the meal; see attachments Observation Data Collection Form, modified from those previously used by [name] and colleagues, and Dyadic Parent-Child Interaction Coding System (DPICS) Form). This portion of the study will be conducted with a subsample of participants during select, in-person cohorts. It will not be completed (i.e. there will be no observations of family interactions) for remote cohorts. Following the brief in-restaurant observation, families in the observed subsample will complete a brief online survey (see attachment: 2023 Observation Parenting Survey). The survey will include a few questions about their experience in the restaurant during the observation as well as a few questions about parenting that used to be part of the Midpoint 1 survey, which was reduced slightly as communicated in prior modifications.

Implementation. At the conclusion of each cohort's data collection period, tracking of intervention components will occur (e.g. number of placemats and toys distributed). In addition, we will monitor implementation during the exposure and post periods (e.g., are study materials displayed as specified). This is not a human subjects research component and therefore it is not discussed further herein.

Table 1. Study outcomes by time point and measure

	Initial Assessment	Midpoint Assessment	Post Assessment
Orders (Primary outcomes)			
Items ordered for children in study sample and their parents	P	P/F	P
Total calories, saturated fat, sodium, and sugar in children's orders	P/N	P/F/N	P/N
Children's meal orders in study restaurants overall during study period	S*	S*	S*
Children's consumption (Secondary outcomes)			
Total calories, saturated fat, sodium, sugar consumed in restaurant	W^N		W/N
Total daily calories, saturated fat, sodium, and sugar consumed			P (recalls)

Other Variables of Interest			
Demographics	P		
Parent perspectives on restaurant/study experience	P	P	P
Child perspectives on restaurant/study experience	C^	P	C^
Observations of family interactions		O**	
Other implementation measures (e.g., tracking placemats)			O***

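### The H1c sales comparison uses a chi-square on individual meals although restaurants are randomised, so its false-positive rate probably exceeds 5% by an amount the documents do not fix

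*Combined protocol and SAP*

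**What the plan says.** Section 4.1 randomises restaurants, not families or meals. Six locations are paired on the income of the surrounding census tracts, and "A location from each pair will be randomized to each study group (intervention, control"). That gives three restaurants per arm.

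Section 1.2 states hypothesis 1c on sales data: "The promoted healthier meals will make up a greater percentage of" kids' meals ordered in intervention restaurants than in controls, across the study period.

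Section 17.1 opens the experimental-phase analysis with a general statement: "Analyses incorporate random effects for restaurant location as required in cluster-randomized trials". The participant-level models for orders and intake then carry that random effect. The sales comparison does not. Its whole specification is one sentence, which begins "We will use sales data and chi-square analyses to compare the percentage of". The outcome is the share of featured meals among all kids' meals sold, compared between the arms over the whole study and again within the recruitment, exposure and redemption periods. No restaurant-level summary, cluster-adjusted chi-square or pairing term is given.

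On status, Table 1 in Section 10.2 places the row for children's "meal orders in study restaurants overall during study period" in the block headed "Orders (Primary outcomes"). Section 2.1, which defines the endpoints, names only children's items ordered and the nutrients in their orders as primary. It does not mention sales share.

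**The concern.** Meals sold in one restaurant share its neighbourhood, customers and staff, so their outcomes are correlated. A chi-square on meals pooled by arm takes its standard error from the number of meals and ignores variation between restaurants. With three restaurants per arm, an ordinary difference between locations can look like an intervention effect, and selling more meals makes this worse. The result at stake is the only restaurant-wide evidence on whether the promotion shifts ordering among all patrons.

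**Working it through.** **The plan's own figure.** The documents give no error rate or sample size for the sales test. They do give 684 participants for calories consumed (Section 17.2), based on alpha .05, 80% power, six clusters and ICC .01.

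- d = (556.6 − 473.3) / √((197.4² + 199.4²)/2) = 83.3/198.4 = 0.42.
- With m = 114 per restaurant, the design effect is DE = 1 + 113 × .01 = 2.13. The effective n per arm is 342/2.13 = 160.6.
- The noncentrality is 0.42 × √(160.6/2) = 3.76. A two-sided noncentral t on 2 × (3 − 1) = 4 df gives 80.0% power.
- 114 is the smallest m that reaches 80%, and 6 × 114 = 684, an exact match.

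The plan's calculation is therefore consistent with inference on six restaurants and 4 df. The sales test drops that basis.

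**Inputs for the sales test.**

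- Alpha is .05 (Section 17.2: "Using these values, an alpha of .05"), taken as two-sided.
- ICC is .01 from Section 17.2. Applying it to sales is an assumption, so .001 is shown as well.
- Meals per restaurant, m, are not given. Section 5.3 suggests about 3,600 families across the recruitment periods. Spread over six restaurants at one kids' meal each, that is 600. At about 10 families per evening over 8 months (recruitment 3, exposure 2, redemption 3), it is 10 × 240 = 2,400. Both are rough assumptions.

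**Formula.** DE = 1 + (m − 1) × ICC. Actual type I error = 2 × (1 − Φ(1.96/√DE)).

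| m per restaurant | DE, ICC .01 | Error, ICC .01 | DE, ICC .001 | Error, ICC .001 |
|---|---|---|---|---|
| 600 | 6.99 | 46% | 1.60 | 12% |
| 1,000 | 10.99 | 55% | 2.00 | 17% |
| 2,400 | 24.99 | 70% | 3.40 | 29% |

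At ICC .01 the error passes 10% at about 43 meals per restaurant and 20% at about 135.

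An ICC of .01 is not a large spread. At the 6.7% control rate in Section 17.2, it is a between-restaurant SD of √(.01 × .067 × .933) = 2.5 percentage points.

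**Simulation.** Beta-binomial, 40,000 runs, three restaurants per arm drawn independently with equal meal counts. The chi-square error agreed with the formula to within about one percentage point. A t-test on the six percentages (4 df) rejected 4.7% to 5.3% of the time, and a paired t-test on the three pairs (2 df) 4.7% to 5.2%.

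**Power at ICC .01, m from 600 to 2,400.**

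| True percentages | t, 4 df | Paired t, 2 df |
|---|---|---|
| 27.8% vs 6.7% (Section 17.2) | about 99.7% | 89–92% |
| 12.0% vs 6.7% (illustrative assumption) | 36–39% | 23–25% |

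The paired figures include no gain from pairing, because restaurants were drawn independently.

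**The case against.** **The general random-effects sentence covers the sales test.** It shows intent, but a chi-square has no random effect and no other method is named for the sales data. The two statements need to be reconciled.

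**The inputs are uncertain.** This stands. No sales count is given, and the ICC of .01 was set for participant-level outcomes. Evening traffic is not total sales, so m could be higher, but several thousand meals per restaurant has no support in the documents. The error rates are conditional on the inputs, not estimates for this chain.

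**Pairing on income may remove much of the variation.** It may remove some. If it removed 90% of the between-restaurant variance at ICC .01, the error would still be about 12% at 600 meals and 29% at 2,400, the same as at ICC .001.

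**Stronger readings a reader might infer.**

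- *H1c would very likely be declared significant in every period.* This does not follow. At 600 meals in a period the error is about 46% at ICC .01 and 12% at ICC .001. The recruitment period is also largely pre-intervention for general patrons: Sections 4.1 and 10.1 put signs and entrance placemats in the exposure and later periods. A difference during recruitment would read as baseline imbalance, not as support for H1c.
- *A primary endpoint has an invalid test.* Table 1 and Section 2.1 differ on whether sales share is primary, so this cannot be asserted.
- *The trial's main analyses share the flaw.* They do not. The order and intake models carry the restaurant random effect.

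**Conclusion.** The point holds for H1c alone. The named test does not match the unit of randomisation and contradicts the plan's own statement on clustering. Its false-positive rate is about 46% to 70% if the plan's ICC of .01 applies to sales and each restaurant sells 600 to 2,400 kids' meals. At a tenth of that ICC it is about 12% to 29%. The rate would be near 5% only with very few meals or almost no variation between restaurants, and nothing in the documents supports either.

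**What to change.** In Section 17.1, replace the chi-square with a restaurant-level analysis:

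1. For each restaurant, compute the percentage of kids' meals that were featured meals, for the whole study period and for each of the three periods.
2. Compare arms with a t-test on the six percentages (4 df). Specify a pair-matched t-test on the three within-pair differences (2 df) as the pair-aware version or as a sensitivity analysis, and state in advance which leads.
3. Treat the recruitment-period comparison as a baseline check.
4. Change from recruitment can be a supporting analysis. So can change from the parallel prior-year sales (Section 10.2), if the featured items were sold then. Neither should replace the main comparison, because H1c concerns the percentage across the study period. These change scores were not simulated here. Enrolled families receive placemats and cards after baseline, so the recruitment baseline may also be slightly contaminated.
5. State whether sales share is primary, so that Table 1 and Section 2.1 agree.

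An exact randomisation test is not a workable substitute: with three pairs its smallest two-sided p-value is 2/8 = 0.25.

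The change needs no new data or recruitment. Its cost is wider intervals and the loss of power for modest effects shown above. The chi-square would reject 92% to 97% of the time at 12.0% versus 6.7%, but that is not usable power in a test that rejects 46% to 70% of the time under the null.
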